6.6.6 Medical History

Medical history will be summarized by MedDRA coding system (version 18.0 or later) SOC, high level term (HLT), and PT. A patient contributes only once to the count for a given condition (overall, by SOC, by HLT, by preferred term). Listing will be provided including medical condition or event, start date and end date.

6.6.7 Concomitant Medications

Concomitant medication is defined as all medications other than study drug administered to a patient with the medication taken after first fitusiran dose for fitusiran arm or after Day 1 visit for the on-demand arm.

Concomitant medications will be coded using the WHO Drug Dictionary (version in use at the time of database lock). Results will be tabulated by anatomic therapeutic class (ATC) and preferred term.

Concomitant medications collected through treatment period will be tabulated by treatment arm and summarized separately for the bleeding treatment medications (as captured in the eDiary) and other medications (as captured in the CRF). Any medications that did not end prior to first fitusiran dose for fitusiran arm or prior to Day 1 visit for on-demand arm will be included. If an end date is missing or the medication is ongoing, the medication will be included.

6.7 Anti-Drug Antibody Analysis

The ADA population includes all patients in the safety analysis set with at least one post baseline ADA result. Number of patients testing positive for ADA pre-study-drug (baseline positive) and post-study-drug administration will be summarized by Hemophilia type (A/B) and incidence of ADA positivity will be presented by frequency and as a percent by Hemophilia type and across all patients. In addition, maximum ADA titer and range of titer values will be presented by Hemophilia type and across all patients.

8 APPENDICES

8.1 Questionnaire/Scoring

8.1.1 Haem-A-QOL and Haemo-QOL

The Haem-A-QOL and Haemo-QOL questionnaires are psychometrically tested QOL assessment instruments for patients with hemophilia.

The Haem-A-QOL will be provided to patients ≥ 17 years of age, and includes 46 items contributing to 10 QOL domains (physical health, feelings, view of yourself, sports and leisure, work and school, dealing with hemophilia, treatment, future, family planning, partnership and sexuality). Scoring for each item is based on a 5-point Likert scale (never, rarely, sometimes, often, and all the time), and higher scores represent greater impairment.

8.1.2 Treatment Satisfaction Questionnaire for Medication (TSQM) domain scores

The Treatment Satisfaction Questionnaire for Medication (TSQM) will assess patient satisfaction with treatment. The TSQM is a validated psychometric tool that provides a general measure of patient satisfaction with medication.

The TSQM Scale scores will be computed by adding the items loading on each factor. The lowest possible score is subtracted from this composite score and divided by the greatest possible score minus the lowest possible score. This provides a transformed score between 0 and 1 that should be multiplied by 100; see [Table 2](#). Note that only one item may be missing from each scale before the subscale should be considered invalid for that respondent.

Table 2: TSQM Scale Scores

Factor	Calculation	In case of missings
Effectiveness	$(((\text{Item 1} + \text{Item 2} + \text{Item 3}) - 3) \text{ divided by } 18) * 100$	If one item is missing: $(((\text{Sum}(\text{Item 1?} + \text{Item 2?} + \text{Item 3?})) - 2) \text{ divided by } 12) * 100$
Convenience	$([\text{Sum}(\text{Item 4 to Item 6}) - 3] \text{ divided by } 18) * 100$	If one item is missing: $(((\text{Sum}(\text{Item4? to Item6?})) - 2) \text{ divided by } 12) * 100$
Globel Satisfaction	$([\text{Sum}(\text{Item 7 to Item 9}) - 3] \text{ divided by } 14) * 100$	If either Item 7 or 8 is missing: $(((\text{Sum}(\text{Item7? to Item9?})) - 2) \text{ divided by } 10) * 100$ If Item 9 is missing: $(((\text{Sum}(\text{Item7 and Item8})) - 2) \text{ divided by } 8) * 100$

8.1.3 Haemophilia Activities List (HAL) / Paediatric HAL (pedHAL) score

The HAL and pedHAL questionnaires will assess subjective functional ability to perform activities of daily living. The HAL will be assessed in patients ≥ 18 years of age, and the pedHAL will be assessed in patients < 18 years of age.

HAL scores can be calculated for each of the seven domains of the HAL. Additionally, three component scores can be calculated (Activities involving the Upper Extremities, Basic activities involving the Lower Extremities and Complex activities involving the Lower Extremities) as well as an overall score. If there is missing item score within a domain or a component, the normalized score for that domain or component will be calculated based on the number of items answered if at least 50% of those scores are non-missing and otherwise it is set to missing. Before summarizing the individual item scores, recoding is required (see [Table 3](#)); a higher raw score represents more functional limitations; possible scoring ranges are given ([Table 4](#)). Normalized scores for the domains, components, and the full questionnaire can also be obtained. Missing values are controlled for and the possible scores range from 0 to 100, where 0 represents the worst possible functional status and 100 the best possible functional status ([Table 5](#)).

Table 3: Recoding

Score	Recode	Meaning
8	0	N/A
1	6	Impossible
2	5	Always problems
3	4	Mostly problems
4	3	Sometimes problems
5	2	Rarely problems
6	1	Never problems

Table 4: Scores

Score		Items	Score range
Lying / sitting / kneeling / standing	LSKS	1-8 (8)	8 - 48
Functions of the legs	LEGS	9-17 (9)	9 - 54
Functions of the arms	ARMS	18-21 (4)	4 - 24
Use of transportation	TRANS	22-24 (3)	3 - 18
Self care	SELFC	25-29 (5)	5 - 30
Household tasks	HOUSEH	30-35 (6)	6 - 36
Leisure activities and sports	LEISPO	36-42 (7)	7 - 42
Upper Extremity Activities	UPPER *	(9)	9 - 54
Basic Lower Extremity Activities	LOWBAS **	(6)	6 -36
Complex Lower Extremity Activities	LOWCOM ***	(9)	9 - 54
Sum score	SUM 1-42	(42)	42 - 252

* Items for UPPER-component: 18, 19, 20, 21, 25, 26, 27, 28, 29. (9 items)

** Items for LOWBAS-component: 8, 9, 10, 11, 12, 13. (6 items)

*** Items for LOWCOM-component: 3, 4, 6, 7, 14, 15, 16, 17, 22. (9 items)

Table 5: Normalization

Score	Normalisation
LSKS	$100 - ((\Sigma 1-8 - \text{valid}) * (100/(5 * \text{valid})))$
LEGS	$100 - ((\Sigma 9-17 - \text{valid}) * (100/(5 * \text{valid})))$
ARMS	$100 - ((\Sigma 18-21 - \text{valid}) * (100/(5 * \text{valid})))$
TRANS	$100 - ((\Sigma 22-24 - \text{valid}) * (100/(5 * \text{valid})))$
SELFC	$100 - ((\Sigma 25-29 - \text{valid}) * (100/(5 * \text{valid})))$
HOUSEH	$100 - ((\Sigma 30-35 - \text{valid}) * (100/(5 * \text{valid})))$
LEISPO	$100 - ((\Sigma 36-42 - \text{valid}) * (100/(5 * \text{valid})))$
UPPER	$100 - ((\Sigma 18-21; 25-29 - \text{valid}) * (100/(5 * \text{valid})))$
LOWBAS	$100 - ((\Sigma 8-13 - \text{valid}) * (100/(5 * \text{valid})))$
LOWCOM	$100 - ((\Sigma 3-7; 14-17; 22 - \text{valid}) * (100/(5 * \text{valid})))$
SUM	$100 - ((\Sigma 1-42 - \text{valid}) * (100/(5 * \text{valid})))$

"valid" = number of items scored within the specific domain/component.

Items with "n/a"-response are to be considered NOT valid

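### The normalization formula for the HAL complex lower extremity component sums ten items, but the SAP defines that component as nine

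*SAP*

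**What the plan says.** SAP section 8.1.3 sets out HAL scoring in steps: recode each item (Table 3), sum it into domains and components (Table 4), and normalize (Table 5).

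- **Definition.** The LOWCOM row of Table 4 gives nine items and a raw range of 9 to 54. Its footnote lists them: "Items for LOWCOM-component: 3, 4, 6, 7, 14, 15, 16, 17, 22. (9 items". Item 5 is absent.
- **Formula.** The LOWCOM row of Table 5 sums items as "\Sigma 3-7; 14-17; 22 - \text{valid" before scaling by 100/(5 × valid).
- **Meaning of *valid*.** The note under Table 5 defines it as the "number of items scored within the specific domain/component". Items answered n/a "response are to be considered NOT valid".
- **Range.** The text states that "possible scores range from 0 to 100, where 0 represents the worst possible functional status", with 100 the best.
- **Missing items.** A domain or component is scored if "at least 50% of those scores are non-missing".

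SAP section 6.3.3.2 then has the overall, component and domain scores, and their changes, summarized by visit.

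**The concern.** Table 5 is what a programmer will code. Its LOWCOM row brings in an item that the definition leaves out, so the number produced is not the component named. The way *valid* is defined makes this worse: read literally, the sum runs over ten items while the divisor counts at most nine, and the result no longer fits the 0 to 100 scale.

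Two programmers working independently from this section could use nine or ten items in the sum, and nine or ten in the divisor, and report different scores for the same patient. The HAL is given to patients aged 18 or over. With about 5 adolescents among about 54 planned patients, most of the trial population would be scored with this formula where the questionnaire is available.

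**Working it through.** **Inputs (all from SAP 8.1.3).** Recoded items run from 1 (never problems) to 6 (impossible), with n/a recoded 0. The formula is score = 100 − (sum − valid) × 100/(5 × valid).

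**Step 1: reproduce the SAP's own range.** With the nine footnote items, all answered, the raw sum runs from 9 × 1 = 9 to 9 × 6 = 54.

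- Best: 100 − (9 − 9) × 100/45 = 100.
- Worst: 100 − (54 − 9) × 100/45 = 0.

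The nine-item list therefore gives the stated 9 to 54 and 0 to 100 exactly.

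**Step 2: count the items in Table 5.** Items 3 to 7 are five, 14 to 17 are four, and 22 is one: 5 + 4 + 1 = 10. The extra item is item 5, and the raw sum runs from 10 to 60. The item lists of Tables 4 and 5 were compared for all 11 scores. Only LOWCOM differs.

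**Step 3: literal reading, ten items summed and *valid* = 9.**

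- Best: 100 − (10 − 9) × 100/45 = 97.8.
- Worst: 100 − (60 − 9) × 100/45 = −13.3.
- Item 5 lowers the score by its recoded value × 100/45, that is by 2.2 (recode 1) to 13.3 (recode 6).
- With item 5 at 6, the score turns negative once the nine-item sum reaches 49: 100 − (55 − 9) × 100/45 = −2.2. The nine-item score for that patient is 100 − (49 − 9) × 100/45 = 11.1.
- With missing items the floor drops further. The 50% rule requires at least 5 of 9. With five component items and item 5 all at 6, the sum is 36 and the score is 100 − (36 − 5) × 100/25 = −24.0.

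**Step 4: alternative reading, ten items summed and *valid* = 10.** The range is 0 to 100. With all items answered, the score equals 0.9 × (nine-item score) + 0.1 × (item 5 on the 0 to 100 scale), so the error is one tenth of the gap between item 5 and the other nine.

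- Nine items at 1 and item 5 at 6: 100 − (15 − 10) × 100/50 = 90 instead of 100.
- Nine items at 6 and item 5 at 1: 100 − (55 − 10) × 100/50 = 10 instead of 0.
- A gap of 20 points: an error of 2 points.

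**Step 5: change from baseline under the literal reading, all nine component items answered.** The error is 2.22 × the change in item 5. It is zero if item 5 is stable, at most 5 × 100/45 = 11.1 if item 5 is answered at both visits, and at most 13.3 if it is answered at only one.

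**The case against.** The mismatch itself is not in dispute. The strongest objections concern its consequences.

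- **The out-of-range result needs a mixed coding.** A programmer who treats the Table 5 list as the component would count *valid* over the same ten items and stay within 0 to 100. One who follows the footnote gets the defined score. This stands as a condition on the range claim. The mixed coding is nevertheless what the SAP's definition of *valid* literally produces, and the ten-item alternative still yields a different component.
- **The figures are extremes.** This stands. Typical errors would be smaller, the range of −13.3 to 97.8 applies only when all ten items are answered, and a patient with item 5 as n/a gets the nine-item score.
- **Item 5 is a near neighbour.** It lies in the lying, sitting, kneeling and standing domain (items 1 to 8), as do LOWCOM items 3, 4, 6 and 7. It is outside the component but not remote from it, so it may often move with the others.
- **Little depends on it.** No model or test is planned for HAL scores, and HAL is not in the hierarchy of SAP section 5.7. This stands and limits the importance.
- **The documents do not reproduce the scoring manual.** The item count, the raw range and the footnote all point to nine items. A slip that shortened 3-4; 6-7 to 3-7 would explain the row, but nothing in the SAP proves it.

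**Conclusion.** The concern holds. Table 5 contradicts Table 4 and its footnote on which items make up LOWCOM. Coded as written, it gives a score that is not the defined component whenever item 5 is answered, except where, with *valid* counted over ten, item 5 happens to equal the average of the other answered items.

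The size depends on how *valid* is counted. Over the nine defined items, the score is 2.2 to 13.3 points too low when all items are answered and can fall below zero. Over ten items, it is off by at most 10 points either way and stays in range.

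This is a minor point. It affects one of three HAL components in a descriptive exploratory summary. The seven domain scores, the other two components and the overall score are correct as written, and no primary, secondary or safety conclusion can change. The contradiction rests on no outside assumption. That nine items is the intended list is an inference from three agreeing statements in the SAP.

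**What to change.** In the LOWCOM row of Table 5, replace the sum with items 3, 4, 6, 7, 14 to 17 and 22, and state that *valid* is counted over those nine items. This restores the raw range of 9 to 54 and the normalized range of 0 to 100. Confirm the list against the instrument's scoring manual before finalizing. If the manual were to include item 5, Table 4 and its footnote would have to change instead.

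The cost is one corrected line in the SAP and a check of any scoring code already written. Data collection and the other analyses are unaffected.

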8.1.4 EuroQol-5 dimension 5 level (EQ-5D-5L) score

The EQ-5D-5L is a standardized instrument for use as a measure of QoL outcome. It consists of a descriptive system and a visual analog scale (VAS).

- 1) EQ-5D descriptive system: has 5 dimensions (mobility, self-care, usual activities, pain/discomfort, anxiety/depression) with 5 levels (no problems, slight problems, moderate problems, severe problems, and extreme problems).

- 2) EQ-5D VAS: is a continuous score ranging from 0 to 100.
- 3) EQ-5D Valuation index: The information of the 5 dimensions of the descriptive system summarized into one index. The EQ-5D-5L index value is calculated using the crosswalk link function and the individual responses to the EQ-5D5L descriptive system. If any of the 5 dimensions have missing values at a given time point, the index value will not be computed.

8.2 List of search terms for COVID-19 (MedDRA v23.0)

Code	PT	Primary SOC
10084510	N/A	Infections and infestations
10084459	Asymptomatic COVID-19	Infections and infestations
10084467	Asymptomatic COVID-19	Infections and infestations
10053983	Coronavirus infection	Infections and infestations
10051905	Coronavirus infection	Infections and infestations
10084382	COVID-19	Infections and infestations
10084268	COVID-19	Infections and infestations
10084401	COVID-19	Infections and infestations
10084270	COVID-19	Infections and infestations
10084272	COVID-19	Infections and infestations
10084381	COVID-19 pneumonia	Infections and infestations
10084380	COVID-19 pneumonia	Infections and infestations
10084383	COVID-19 pneumonia	Infections and infestations
10084451	Suspected COVID-19	Infections and infestations
10084452	Suspected COVID-19	Infections and infestations
10084461	SARS-CoV-2 carrier	Infections and infestations
10084456	Exposure to SARS-CoV-2	Injury, poisoning and procedural complications
10084394	Occupational exposure to SARS-CoV-2	Injury, poisoning and procedural complications
10084353	Coronavirus test	Investigations
10084269	Coronavirus test negative	Investigations
10070255	Coronavirus test positive	Investigations
10084508	SARS-CoV-2 test	Investigations
10084507	SARS-CoV-2 test	Investigations
10084500	SARS-CoV-2 test	Investigations
10084441	SARS-CoV-2 test	Investigations
10084499	SARS-CoV-2 test	Investigations
10084431	SARS-CoV-2 test	Investigations
10084356	SARS-CoV-2 test	Investigations
10084501	SARS-CoV-2 test	Investigations
10084493	SARS-CoV-2 test	Investigations
10084434	SARS-CoV-2 test	Investigations
10084440	SARS-CoV-2 test	Investigations

Code	PT	Primary SOC
10084354	SARS-CoV-2 test	Investigations
10084481	SARS-CoV-2 test false negative	Investigations
10084480	SARS-CoV-2 test false negative	Investigations
10084495	SARS-CoV-2 test negative	Investigations
10084492	SARS-CoV-2 test negative	Investigations
10084504	SARS-CoV-2 test negative	Investigations
10084436	SARS-CoV-2 test negative	Investigations
10084502	SARS-CoV-2 test negative	Investigations
10084432	SARS-CoV-2 test negative	Investigations
10084357	SARS-CoV-2 test negative	Investigations
10084509	SARS-CoV-2 test negative	Investigations
10084494	SARS-CoV-2 test negative	Investigations
10084435	SARS-CoV-2 test negative	Investigations
10084438	SARS-CoV-2 test negative	Investigations
10084273	SARS-CoV-2 test negative	Investigations
10084505	SARS-CoV-2 test positive	Investigations
10084496	SARS-CoV-2 test positive	Investigations
10084498	SARS-CoV-2 test positive	Investigations
10084437	SARS-CoV-2 test positive	Investigations
10084503	SARS-CoV-2 test positive	Investigations
10084433	SARS-CoV-2 test positive	Investigations
10084355	SARS-CoV-2 test positive	Investigations
10084491	SARS-CoV-2 test positive	Investigations
10084497	SARS-CoV-2 test positive	Investigations
10084442	SARS-CoV-2 test positive	Investigations
10084439	SARS-CoV-2 test positive	Investigations
10084271	SARS-CoV-2 test positive	Investigations
10084458	COVID-19 prophylaxis	Surgical and medical procedures
10084460	COVID-19 treatment	Surgical and medical procedures
10084457	COVID-19 immunisation	Surgical and medical procedures
10084464	COVID-19 immunisation	Surgical and medical procedures
10084465	COVID-19 immunisation	Surgical and medical procedures
10084463	COVID-19 immunisation	Surgical and medical procedures
10084466	COVID-19 immunisation	Surgical and medical procedures
10084462	COVID-19 immunisation	Surgical and medical procedures
10084469	Patient isolation	Surgical and medical procedures
10084470	Quarantine	Surgical and medical procedures
10084468	Quarantine	Surgical and medical procedures
